	7.1 Study Subjects4				
	.2	General Methodology			
	.3	Center Pooling5			
7	.4	Handling of Missing, Unused, and Spurious Data and Dropouts5			
7	.5	Adjustments for Multiple Comparisons6			
7	.6	Demographic and Other Baseline Characteristics			
7	.7	Treatment Characteristics6			
7	.8	Interim Analyses6			
7	.9	Evaluation of Objectives6			
7	.10	Safety Evaluation			
8.	Valid	dation Requirements			
ımm	arv of	Changes Front Rookmark not defined			

Revision 1.0 Page 3 of 7

1. Version History

Version	Summary of Changes	Author(s)/Title
1.0	Not Applicable, New Document	[name], Senior biostatistician

2. List of Abbreviations and Definitions of Terms

Abbreviation	Definition
AE	Adverse Event
CCE	Colon Capsule Endoscopy
CIP	Clinical Investigation Plan
CRC	Colorectal Cancer
FAS	Full Analysis Set
MB-MMX	Per-oral Methylene Blue Formulation
PPAS	Per Protocol Analysis Set
SAP	Statistical Analysis Plan
95%CI	95% Confidence Interval

3. Introduction

Given Imaging Ltd. (an indirect wholly owned subsidiary of Medtronic plc.) is sponsoring the SPICE study, a prospective single-center open-label pilot clinical study. The purpose of this study is to evaluate the technical feasibility of mucosal staining during capsule endoscopy (PillCam™ COLON2) procedure when using MB-MMX as mucosal enhancement technique. The study will be conducted in population with high risk for CRC. The MDT20062 SPICE Study Clinical Investigation Plan (CIP) Ver.4.0 16-Jun-2022 document was used to formulate this SAP.

4. Study Objectives

Primary objective - To demonstrate an effective polyp enhancement during a Colon Capsule Endoscopy (CCE) procedure when using MB-MMX as a contrast- enhancement technique.

Secondary objective - To evaluate the safety of CCE procedure while using MB-MMX

5. Investigation Plan

This is a single-center, prospective, non-randomized, open label pre-market clinical trial, designed to evaluate the technical feasibility during CCE procedure, when using MB-MMX as a contrast- enhancement technique of mucosal staining in CRC high risk population. Up to 15 subjects, 45-75 years old, classified as being at high risk for CRC, will be enrolled in 1 site in Spain. Subjects will undergo a standard bowel preparation (4L PEG), including 200 mg Methylthioninium chloride, corresponding to 8 tablets of 25 mg MB-MMX (per product's instructions for use) and will undergo a CCE procedure. An experienced

Gastroenterologist will read the CCE procedure and complete a subjective questionnaire, to evaluate mucosal enhancement during a CCE procedure, when using MB-MMX as a contrast-enhancement technique.

This is an initial pilot study with descriptive endpoints.

6. Determination of Sample Size

[figure not shown]
This is a single-center, prospective, non-randomized clinical trial aimed to evaluate technical feasibility with descriptive endpoint(s), thus, no formal sample size was calculated and up to 15 patients are planned to be enrolled to this study. No interim analysis is planned.

7. Statistical Methods

7.1 Study Subjects

7.1.1 Disposition of Subjects

The following flow diagram will be presented

7.1.2 Clinical Investigation Plan (CIP) Deviations

Except from the eligibility criteria and informed consent deviations, bowel preparation related deviations and MB-MMX intake deviations will be reported.

The deviations will be presented with a designated table (for more than 1 deviation for the entire trial), stating the relevant information (subject#, deviation date, deviation description, result of the deviation {excluded from the per-protocol analysis set for example}.

Revision 1.0 Page 5 of 7

7.1.3 Analysis Sets

Full Analysis Set (FAS) - includes all enrolled subjects who:

- Signed the informed consent and
- Satisfied the eligibility criteria and
- Ingested the PillCam™ COLON2 capsule

Full analysis set (FAS) will include all of the subjects the ingested the capsule and will be used for subject disposition, population and procedures description, for performance and for Safety analyses.

Per Protocol Analysis Set (PPAS) will include a subset of the FAS, which includes only subject who have demonstrated all of the following:

- Subjects' compliance to the bowel prep regimen/MB-MMX administration is ≥75% according to each of the following criteria:
 - Total volume of bowel prep material (PEG) consumed is ≥3L (out of 4L in total)
 - Intake of ≥6 MB-MMX tablets (out of total of 8 tablets)
- No major deviations related to Eligibility Criteria and/or Informed Consent.
- The capsule reached the colon during the procedure.
- Raw data has been generated for the CE procedure.

Any deviation from specified statistical plan will be in addition to "per protocol" analysis and will be reported as such. Post-hoc analysis will be conducted according to the existing data gathered, if necessary.

In addition, as there was an amendment to the CIP, and as a result, the 5 first subjects received a split dose PEG regimen and the rest received a single dose of PEG regimen, a sub-group analysis will be performed as well according to the prep regimen.

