Medtronic is responsible for analyzing deviations, assessing their significance, and identifying any additional corrective and/or preventive actions (e.g. amend the CIP, conduct additional training, terminate the investigation). Repetitive or serious investigator compliance issues may result in initiation of a corrective action plan with the investigator and study site, and in some cases, may necessitate suspending enrollment until the problem is resolved or ultimately terminating the investigator's participation in the study. If further escalation is needed, it may result in Corrective and Preventive Action (CAPA), suspension, or termination. If it is determined that there is investigator fraud, or strong evidence of fraud, the course of action may include, but is not limited to: potential exclusion from analyses, site closure, notification of the responsible EC of the actions to be taken, notification of key stakeholders and/or study team of the actions to be taken, notification of appropriate CA and/or restrictions on future participation in clinical studies. The Sponsor will provide reports to investigator summarizing information on deviations that occurred at the investigational study site on a periodic basis.

Major deviations are defined as deviations with respect to:

• Failure to obtain proper IC

Version 4.0

• Subject's eligibility criteria not met

Bowel preparation related deviations are common and expected. Deviations related to bowel preparation consumption/MB-MMX intake will be specifically defined for the study and captured accordingly in the eCRF. For further details please refer to Appendix B: Bowel Preparation/MB-MMX administration Deviations.

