## MDT20062 SPICE Clinical Investigation Plan Version 4.0 Version Date: 16Jun2022 Page 34 of 75 Medtronic

#### 10.15. Subject Exit, Withdrawal or Discontinuation

A study exit eCRF is required for all subjects. The reason for study exit, including screen failure, will be documented on the applicable eCRF and in the subject file. The Sponsor must be informed of each withdrawal case. Prior to exiting a subject from the study, it is recommended to follow the subject until all ongoing device and/or procedure related AEs are resolved or unresolved with no further actions planned. At the completion of the follow-up visit, the subject will be exited from the study. A follow-up eCRF and a Study Exit eCRF will to be completed. Upon exiting from the study, no further study data will be collected, or study visits will occur for the subject, unless the subject has been referred to a colonoscopy procedure post the CCE procedure (de-identified colonoscopy report and images/videos may be collected) and/or AE follow up is required.

Subjects will be informed that they have the right to withdraw from the study at any time, without prejudice to their medical care, and are not obliged to state their reasons.

If the subject wishes to exit from the study (i.e. the subject revokes consent), the study site is required to document the reason for exit on the Exit eCRF. In addition, study site shall follow the regulations set forth by the governing EC. Per ISO14155 guidance, permission may be requested to follow up with the subject outside of the study, due to withdrawal based on issues related to the investigational feature safety or performance.

The investigator may withdraw a subject from the assigned study at any time if any of the following situations arise:

- 1. Subject did not provide consent/ withdrawal of informed consent by the subject
- The Principal Investigator deems that it is in the subject's best interest to withdraw from the study for subject's safety.
- 3. Subject's death
- 4. Occurrence of a Serious Adverse Device Effect (SADE), or severe side effects
- 5. Presence or appearance of any of the exclusion criteria/inclusion criteria not met
- 6. A significant CIP violation, as determined either by the sponsor or the investigator
- 7. Subject noncompliant with study procedures/visits

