#### 13.1. General Aspects of Analysis

Data analysis will be performed by the sponsor and/or designee.

The analysis will include all of the available information. Demographic and other characteristics will be provided. Summary statistics (arithmetic mean, standard deviation, and range for quantitative variables) will be presented for the total study population. Frequency tables for qualitative data will be provided. All confidence intervals will be presented as 95% confidence intervals unless otherwise stated. For each of the objectives the available data will be summarized, and missing data will be discussed. The main analysis of the study objectives will be based on available data and missing data will not be imputed.

Two analysis sets will be used for the statistical analysis. The definition of each is defined below:

Full Analysis Set (FAS). FAS includes all enrolled subjects:

MDT20062 SPICE Clinical Investigation Plan				
Version 4.0	Version Date: 16Jun2022	Page 50 of 75		Medtronic

- Who signed the informed consent and
- Who satisfied the eligibility criteria
- Ingested the PillCam™ COLON2 capsule

FAS will be used for subject disposition, population and procedures description, for performance and for Safety analyses.

**Per Protocol Analysis Set (PPAS):** PPAS is a subset of the FAS, which includes only subject who have demonstrated all of the following:

- Subjects' compliance to the bowel prep regimen/MB-MMX administration is ≥75% according to each of the following criteria:
  - Total volume of bowel prep material (PEG) consumed is ≥3L (out of 4L in total)
  - Intake of ≥6 MB-MMX tablets (out of total of 8 tablets)
- No major deviations related to Eligibility Criteria and/or Informed Consent
- The capsule reached the colon during the procedure
- Raw data has been generated for the CE procedure

Any deviation from specified statistical plan will be in addition to "per protocol" analysis and will be reported as such. Post-hoc analysis will be conducted according to the existing data gathered, if necessary.

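### SAP 7.1.3 defines the full analysis set in two ways; read literally, its bullet list takes a subject who swallowed the capsule and was later found ineligible out of the safety and performance results

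*SAP*

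**What the plan says.** SAP 7.1.3 opens with a list: the FAS is made up of enrolled subjects who signed consent, "Satisfied the eligibility criteria and" swallowed the capsule. The sentence straight after the list gives a different rule: "Full analysis set (FAS) will include all of the subjects the ingested the capsule". The same sentence assigns the FAS to disposition, "population and procedures description, for performance and for Safety analyses". No other set is assigned to safety.

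Protocol 13.1 carries the list only ("Who satisfied the eligibility criteria") and has no sentence admitting everyone who ingested.

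In both documents the PPAS is nested in the FAS. The SAP says it "will include a subset of the FAS, which includes only subject who have demonstrated all of the following", and one of the conditions is "No major deviations related to Eligibility Criteria and/or Informed Consent". Protocol 10.14 defines the relevant major deviation as "Subject's eligibility criteria not met". Protocol 10.15 lists among the reasons for withdrawal "Presence or appearance of any of the exclusion criteria/inclusion criteria not met". Protocol 9.2 and 10.10 treat a subject as enrolled once consent is signed and the criteria have been judged to be met.

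**The concern.** Enrolment already requires a finding of eligibility at screening, so the two rules give the same set in most cases. They part when someone passes screening, swallows the capsule, and is afterwards found to breach a criterion. The protocol foresees this, both as a major deviation and as a ground for withdrawal.

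Under the sentence, that subject stays in the FAS and is removed at the PPAS step. Under a literal reading of the list, the subject is in neither set. An exposed subject would then be missing from the percentage with at least one adverse event, from the polyp contrast percentage and from the segment ratings. The study is open-label and is analysed by the sponsor or its designee, so whether a criterion was met could be settled after the subject's outcome is known. A safety denominator should not depend on that decision.

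**Working it through.** **Inputs.** At most 15 subjects (SAP 6). Five segments per subject and up to 75 segments in total (SAP 7.9). Safety measure: percentage of cases with at least one adverse event, with a 95% CI (SAP 7.9, Protocol 13.4). The number of ineligible ingesters and the adverse event rates are assumptions, as the documents give neither. The SAP names no interval method; Clopper-Pearson is assumed.

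**The plan's own figure.** 15 × 5 = 75 segments, as stated. This maximum requires all 15 subjects to be in the set.

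**Set logic for a consented subject who ingested.**

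| Subject | FAS by list | FAS by sentence | PPAS eligibility condition under list | PPAS eligibility condition under sentence |
|---|---|---|---|---|
| Eligible | in | in | no effect | no effect |
| Found ineligible, consent proper | out | in | no effect (already out) | removes the subject |

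Under the list, the eligibility half of the PPAS condition changes membership in no combination. The consent half can still act, for example where a form was signed but consent was not properly obtained.

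**Effect on counts.** With k ineligible ingesters out of 15, the list leaves 15 − k subjects and 5 × (15 − k) segments; the sentence keeps 15 and 75.

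| k | Subjects by list | Segments by list | Share of exposed subjects lost |
|---|---|---|---|
| 0 | 15 | 75 | 0% |
| 1 | 14 | 70 | 1/15 = 6.7% |
| 2 | 13 | 65 | 2/15 = 13.3% |
| 3 | 12 | 60 | 3/15 = 20.0% |

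**Effect on the safety percentage**, with one ineligible subject who has an adverse event:

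| Assumed setting | By sentence (exact 95% CI) | By list (exact 95% CI) |
|---|---|---|
| Only event in the study | 1/15 = 6.7% (0.2–31.9%) | 0/14 = 0% (0–23.2%) |
| Five subjects with events | 5/15 = 33.3% (11.8–61.6%) | 4/14 = 28.6% (8.4–58.1%) |
| Ten subjects with events | 10/15 = 66.7% (38.4–88.2%) | 9/14 = 64.3% (35.1–87.2%) |

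The upper limit for 0/14 is 1 − 0.025^(1/14) = 23.2%. The differences are 6.7, 4.8 (33.3 − 28.6, from unrounded values) and 2.4 percentage points.

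**The case against.** The strongest reply is that the two statements can be reconciled. If satisfying the criteria means having passed the screening decision, a subject later found in breach stays in the FAS, the PPAS condition does its work, and the list and sentence agree. SAP 7.1.2 supports this, since its example of the result of a deviation is exclusion from the per-protocol set. Alternatively, the sentence may be only a loose lead-in to the uses of the FAS. The first reading is possible, but the eligibility bullet then only repeats what enrolled already means, and deleting it loses nothing. On the second, the list governs and the exposed subject is lost. SAP 7.9 and Protocol 13.4 do not settle it, because they say only that the data are analysed according to the inclusion, exclusion and deviation criteria.

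Some stronger readings are tempting and should be resisted:

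- A reader might infer that eligibility violators are the subjects most likely to have an adverse event. The documents give no such figure. Some criteria do concern safety, but others do not, such as the age range, the risk category and sponsor employment.
- A reader might infer that the whole PPAS deviation condition becomes empty. Only its eligibility half does.
- A reader might take 1/15 against 0/14 as the expected size. Protocol 11.1 lists common dye effects and many preparation symptoms, so a single event in the whole study is an extreme case.
- A reader might fear that the event disappears. It does not: withdrawn subjects' safety data go into the eCRF (Protocol 10.15), SAP 7.4 puts all available data in the listings and tabulations, and SAP 7.1.2 and 7.10 report deviations and deaths. What is exposed is the summary denominator and the performance results.

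**Conclusion.** The conflict is in the current SAP text and should be resolved. It is a stated rule that, taken literally, can give a wrong denominator; it is more than a missing detail.

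Its size is conditional. It is zero if no ineligible subject ingests. Otherwise each such subject accounts for 6.7% of a full study of 15, for five segments, and for any polyps found in that subject. In the illustrations, one such subject with an event moves the safety percentage by 2.4 to 6.7 points, well inside the width of the intervals. No hypothesis or threshold depends on it, because the study is descriptive. The case for acting rests on keeping exposed subjects in the safety set whatever is later decided about their eligibility. That the authors meant the exclusion to act only at the PPAS step is a reasonable inference from the structure of the two sets, but the documents do not say so.

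**What to change.** Before database lock, delete the eligibility bullet from the FAS in SAP 7.1.3 and reword the sentence after the list to match: all consented subjects who ingested the capsule. Naming consent there matters, because the present sentence also omits the consent condition. Leave the PPAS condition as it is, so that it becomes the only step at which an eligibility deviation removes a subject.

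Protocol 13.1 would then differ from the SAP. Protocol section 13 allows departures from the planned analyses to be noted in the study report, so note it there, or align 13.1 at the next amendment. A protocol change for this alone would require submission to the ethics committee and competent authority (Protocol 15.6), which is more than a one-line edit.

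The SAP change needs no further data or subjects. Its downside is that the performance results may include a subject outside the target population; the PPAS already shows the results without that subject.

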#### 10.1. Schedule of Events & Data collection

The study assessment in table 1 indicates the observations/ assessments/ data collection to be conducted throughout the study period.

Table 1- Schedule of events and data collection:

	Screening/ Enrollment	Preparation	Procedure Visit	Follow Up Visit
↓ Procedure Visit ⇒	V1		V2	V3
Time Schedule (Days)	(-30)-(-3) 	(-3)-0 	0	7±2
Inform consent	Х			
Eligibility criteria	Х			
Demographic data	Χ			
Medical History	Х			
Concomitant medication	Χ		X	
Vital Signs and height/weight measurements	Х		Х	
Urine Pregnancy test (when applicable)	Х	X 		
Provide Preparation materials (including MB-MMX) and subject instructions form	Х			
Low Fiber Diet		X		
Bowel Preparation intake		Х		
MB-MMX intake		X 		
Bowel preparation and MB-MMX compliance verification			Х	
Prucalopride administration			Х	
CCE administration			X	
Device Deficiencies			X	Х
Study Deviations	Х	Х	X	Х
AEs collection		Х	Х	X
Study exit				Х

<sup>1 Screening/enrollment process may start 3-30 days prior to visit 2.

<sup>2Preparation starts 3 days prior to visit 2

<sup>3 Urine Pregnancy test must be performed at day (-1) prior to the bowel prep/MB-MMX intake (when applicable).

<sup>4MB-MMX is administrated at day (-1).

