#### 10.3. PillCam™ Capsule pre-ingestion preparation procedure

The pre-ingestion preparation procedure is similar to colonoscopy or capsule endoscopy standard preparation and is performed in accordance to the labeling of the agents which are being used. In this study MB-MMX tablets will be also administrated to evaluate colonic polyps staining during the CCE procedure. Use of MB-MMX will be according to the product's label.

The preparation procedure will begin with a low fiber diet at days (-3)- (-2) before the CCE, followed by a clear liquid diet, starting from the day before capsule ingestion. At day (-1) prior to the CCE, a urine pregnancy test will be performed (as applicable and prior to prep/MB-MMX administration) and bowel preparation agent will be administrated (single dose) as well as administration of MB-MMX tablets (in accordance to the product's IFU). At the day of CCE procedure, 1 tablet of prucalopride (i.e. Resolor) 1mg will be administrated Prior to the CCE procedure. The subject will be required to consume additional bowel preparation & prokinetic agents during the CCE procedure.

Prior to the CCE procedure, the subjects will be given detailed instructions regarding the preparation regimen, as specified in the subject instructions form that will be provided to the subject during the screening visit.

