## MDT20062 SPICE Clinical Investigation Plan Version 4.0 Version Date: 16Jun2022 Page 65 of 75 Medtronic

#### Appendix B: Bowel Preparation/MB-MMX administration Deviations

Activity	Deviation specifications					
Diet	Complete deviation if:					
restrictions	• Low-fiber diet was not followed at day 2 and day 3 prior to CCE procedure					
	• Clear liquid diet was not followed 24h prior to and during the CCE procedure					
Bowel prep &	Complete deviation if:					
MB-MMX	• MB-MMX intake is less than 8 tablets. If less than 6 tablets- Exclude from the					
schedule and	analysis					
volume	• MB-MMX is taken after less than 1L of PEG.					
	• MB-MMX timing of intake for 2 nd and 3 rd doses is ±10 min from the allowed					
	intervals (as described in Appendix A)					
	• PEG volume consumed is less than 3.5L.					
	• PEG volume consumed is less than 3L.: Exclude from the analysis.					
	● PEG volume consumed is less than 2.5L: No ingestion					
	• PEG consumed during more than 5h/ less than 2h.					
	• Bowel prep consumed prior to Day (-1)— cancel/postpone the procedure.					
Prucalopride	Complete deviation if Prucalopride tablet was not administrated prior to capsule					
Intake	ingestion.					
Capsule	Complete deviation if the capsule was ingested less than 45m or more than 90m					
ingestion	from Prucalopride intake.					
Boosts	Complete deviation if:					
schedule/	Boost consumption started more than 15m from alert**					
volume	• Complete deviation if less than entire volume was consumed***					

\* In case of a PEG volume deviation s, it should be reported as 1 deviation.

\*\*In case a boost consumption was not started within the regimen timelines and a capsule was excreted within 30 minutes from alert, it will not be considered as a deviation.

\*\*\*In case a capsule is excreted during boost consumption, partial volume of boost consumption will not be considered as a deviation.

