3.0	1. Part 11 compliant signature- added when applicable 2. Throughout the document- morning bowel preparation was removed and 2L of PEG were moved to day -1. 3. Prucalopride tablet was added to the regimen 4. Exclusion criteria #17- added per Investigator's discretion 5. Appendix B: Deviations table was updated 6. Appendix D: Subjective Assessment Questionnaire was updated 7. Section 12 was updated	1. Added to reflect that this regulation is not applicable in the study geography (EU) and the documents signed under the study are not submitted to the FDA 2. This change reflects the change in bowel prep regimen- single PEG dose at day -1, instead of spit dose. 3. Added as an agent to support to capsule movement in the colon. 4. Added for clarification 5. Was updated to reflect the current CIP deviations 6. Appendix D: Subjective Assessment Questionnaire was updated to include more rows for polyps (up to 25) 7. for better alignment with ISO 14155:2020 language	1.N/A 2.N/A 3.N/A 4.NA 5.N/A 6.N/A 7.N/A	1.N/A 2.ICF 3.ICF 4.NA 5.N/A 6.N/A 7.N/A	[name]/ CSM
4.0	1. Section 6.1- study duration was extended to 13 months	Duration was     extended to allow     study procedures     completion	1. NA	1. NA	[name]/ CSM

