7.2 General Methodology

This is a single-center, prospective, non-randomized clinical trial designed to evaluate the technical feasibility (descriptive) of mucosal staining during CCE procedure, using MB-MMX, in CRC high risk population. As a result, the methods for analysis will be descriptive in nature (frequency and percent as well as distribution measures such as: mean, standard deviation, median and range). 95% confidence intervals (95%CI) will be presented as well.

In any case of post hoc analysis which will include statistical testing, P-value<0.05 will be considered significant.

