7.9 Evaluation of Objectives

Primary objectives/endpoints analysis

Polyp enhancement

For each subject, the images with polyps that were detected from the COLON2 Capsule Endoscopy procedure will be considered, i.e. the final sample size for this analysis is the number of images with polyps (one image per polyp) - the analyzed unit is the polyp image. For each polyp the reader will indicate if there was a contrast between the polyp and the healthy mucosa (yes/no). Out of the entire polyp images (from all of the subjects together), the percent of colonic polyps which have a visible contrast to the healthy colonic mucosa will be presented along 95%CI.

As this is a descriptive pilot study, no formal hypothesis was formulated. In any case of post hoc analysis which will include statistical testing, P-value<0.05 will be considered significant.

Detrimental effect

For each subject, each of the colonic segments (5 segments per subject) will be evaluated for the interference level of detrimental effects, i.e. the final sample size for this analysis will be up to 75 colonic segments - the analyzed unit is the colonic segment. For each segment the reader will indicate the level of interference according to a 5-point scale (1 =no interference to 5= high interference).

The level of interference refers to the detrimental effects on the visualization of the colonic mucosa during CCE, due to use of MB-MMX (detrimental effect will be considered as any observation, such as an excessive blue dye deposit, dark and dim appearance of the tissue, interfering with tissue visualization). Analysis of this endpoint will include summary statistics (arithmetic mean, standard deviation, median and range) as well as frequency and percent of each scale level.

The rate of colonic segments with high level of interference (i.e. 4-5 levels) out of the entire sample of segments will be presented along 95%CI.

MDT20062 SPICE Statistical Analysis Plan Revision 1.0 Page 7 of 7 Medtronic

Secondary objectives/endpoints analysis

All AEs will be reported by number, type, relatedness (device/procedure), seriousness, severity and duration. All AEs will be captured, regardless of severity. The percent of cases with at least one AE out of the total cases, will be presented with 95%CI. All of the available information will be analyzed according to the CIP criteria (inclusion, exclusion, deviations etc.).

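### Does the SAP's split-dose versus single-dose PEG subgroup need redefining because prucalopride arrived in the same amendment, and do post hoc tests need a clustering rule?

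*SAP*

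**What the plan says.** SAP 7.1.3 adds a subgroup analysis by preparation regimen. It explains that the Protocol was amended and that "the 5 first subjects received a split dose PEG regimen and the rest received a single dose of PEG regimen". It names no endpoint, test or rule of interpretation for the subgroup, and the SAP does not mention prucalopride.

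Protocol section 18 lists two regimen changes under version 3.0: "morning bowel preparation was removed and 2L of PEG were moved to day -1" and "Prucalopride tablet was added to the regimen". The stated reason for the second is to help the capsule move through the colon. The same version also updated the deviation table (Appendix B) and added polyp rows to the reader questionnaire (Appendix D).

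The current Protocol treats prucalopride as part of preparation. Section 10.3 says "1 tablet of prucalopride (i.e. Resolor) 1mg will be administrated Prior to the CCE procedure", and it also appears in the Appendix A schedule. Table 1 lists "Prucalopride administration" at visit 2, and Appendix B has the entry "Complete deviation if Prucalopride tablet was not administrated prior to capsule" ingestion.

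On testing, SAP 7.2 says "In any case of post hoc analysis which will include statistical testing, P-value<0.05 will be considered significant", and SAP 7.9 repeats it. For polyp contrast, SAP 7.9 states that "the analyzed unit is the polyp image". For interference the unit is the colonic segment. Both are pooled over subjects. No formal hypothesis is set.

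**The concern.** The subgroup is a planned output, and its wording names PEG timing alone. If the first five subjects had no prucalopride, then PEG timing, prucalopride and order of enrolment all change at the same point, and no analysis can separate them. A reader who sees two columns headed split dose and single dose could credit a difference to PEG timing. The early cohort is not small: 5/15 = 33% of subjects at full enrolment, and more if fewer enrol.

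The second worry concerns the significance rule. Units from one subject tend to resemble each other. If someone compared the cohorts with an ordinary test on pooled polyps or segments, the test would treat correlated units as independent. The 0.05 rule could then label a chance difference significant, in a pilot that Protocol 6.2 says may lead to a larger study.

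**Working it through.** **What changed and what the SAP discloses**

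| Feature that differs between cohorts | Source | Visible in SAP 7.1.3? |
|---|---|---|
| PEG split, then single dose | Protocol 18, version 3.0 | Yes, named |
| Prucalopride added | Protocol 18, version 3.0 | Not named; part of preparation in Protocol 10.3 and Appendix A |
| Enrolment order | SAP 7.1.3 | Yes, first five against the rest |
| Origin in an amendment | SAP 7.1.3 | Yes, stated |
| Questionnaire rows, deviation table | Protocol 18, version 3.0 | No |

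That the first five had no prucalopride is inferred from the version history; no document states it. Intake is a scheduled visit 2 item and its omission is a listed deviation under the current Protocol, so whoever writes the report can check it.

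**Effect of relabelling.** Calling the groups before and from version 3.0 leaves the same 5 subjects against at most 10, with the same percentages, means and intervals. The table could not support an attribution under either label. At subject level, the exact 95% upper limit after 0 of n events is 1 − 0.025^(1/n): 52% for n = 5 and 31% for n = 10.

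**The plan's own figure.** 15 subjects × 5 segments = 75, which matches SAP 7.9. Split by cohort this is 25 against 50 segments.

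**Post hoc test, if one were run on pooled units.** The documents give no test, intraclass correlation (ICC) or polyp count, so all three are assumed. With m units per subject the design effect is DE = 1 + (m − 1) × ICC, and the actual error of a nominal two-sided 5% test is about 2 × [1 − Φ(1.96/√DE)]. For m = 5:

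- ICC 0.1: DE = 1.4, error about 9.8%
- ICC 0.3: DE = 2.2, error about 18.6%
- ICC 0.5: DE = 3.0, error about 25.8%

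Fisher's exact test is conservative, so its error is lower. Beta-binomial simulation (5 against 10 subjects, no true difference, 10,000 runs per cell) gives these type I errors:

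| Pooled unit | ICC 0 | 0.1 | 0.3 | 0.5 |
|---|---|---|---|---|
| Segments, 20% high interference | 3.5% | 7.3% | 14.9% | 23.7% |
| Segments, 5% high interference | 2.1% | 4.5% | 8.8% | 14.4% |
| Polyps, mean 1 per subject, 70% contrast | 1.7% | 2.1% | 3.2% | 4.2% |
| Polyps, mean 3 per subject, 70% contrast | 3.0% | 5.9% | 11.4% | 17.5% |
| Polyps, mean 6 per subject, 70% contrast | 3.8% | 9.5% | 21.9% | 31.3% |

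The last row deserves little weight. With a Poisson mean of 6, the chance that even one of 15 subjects is polyp-free is 1 − (1 − e^−6)^15, about 4%, whereas Protocol 13.5 assumes that some subjects will have no polyps.

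Permuting subject labels, a standard remedy, held the error at about 3% for segments at a 20% rate (8,000 runs per ICC).

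**The case for a change.** The best argument for acting is that the edit is cheap. Two sentences in the SAP would name the bundle and require any post hoc test to respect the subject, with no Protocol amendment and no new data. The subgroup is pre-specified, the SAP never names prucalopride, and a literal report could carry the incomplete label forward. The significance rule is explicit, and SAP 7.5 treats multiplicity as not applicable, so nothing in the text restrains a naive test.

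What stands is that the description is incomplete. A report author should name both regimen changes and say that their effects cannot be separated. That is ordinary reporting care, and the Protocol supplies the information for it. The documents also give no mechanism by which prucalopride, added for capsule movement, would bias dye contrast or dye interference in a known direction.

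The inflation figures are sound on their assumptions, but they describe a test the SAP does not plan, on units it does not prescribe for such a test. Leaving the method of an unplanned test unwritten is normal in a descriptive pilot. Clustering does bear on a stated output elsewhere, namely the planned 95% confidence intervals on pooled polyps and segments in SAP 7.9. That is a separate question, and a rule for post hoc p-values would not touch those intervals.

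**Conclusion.** No change to the plan follows. The subgroup wording omits prucalopride, but an analyst can fill that gap from the Protocol, and filling it changes no tabulated value for the 5 against at most 10 subjects. The SAP makes no claim that a cohort difference would be due to PEG timing, and it already discloses the amendment and the enrolment order.

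The clustering point is conditional on two choices the SAP does not make: testing the cohorts, and ignoring the subject when doing so. If both were made, the error could reach about 15% to 24% for segments at a 20% rate with an ICC of 0.3 to 0.5. It stays at or below 5% when units are independent or polyps are few. No primary or secondary estimate depends on it.

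This conclusion assumes that the subgroup is reported descriptively, as SAP 7.2 sets out, and that the regimen each subject received is taken from the records, since the absence of prucalopride in the first five is only inferred.
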